8.3 Lost to Follow Up

A subject will be considered lost to follow-up if we are unable to contact them after four attempts in 4 weeks.

The following actions must be taken if a subject fails to return to the clinic for a required study visit:

- The site will attempt to contact the subject, reschedule the missed visit within five business days, counsel the subject on the importance of maintaining the assigned visit schedule, and ascertain if the subject wishes to and/or should continue in the study.
- Before a subject is deemed lost to follow-up, the investigator or designee will make every effort to regain contact with the subjects. These contact attempts will be documented in the subject's medical record or study file.
- Should the subject continue to be unreachable, he or she will be considered to have withdrawn from the study with a primary reason of lost to follow-up.

9. Correlative/Special Studies

Not applicable.

10. Measurement of Effect

Not applicable

11. Data Reporting / Regulatory Considerations

11.1 Data Collection

The data collection plan for this study is to utilize REDCap to capture all treatment, toxicity, and efficacy data for all enrolled subjects.

11.1.1 REDCap

REDCap (Research Electronic Data Capture) is a free data management software system that is fully supported by the Weill-Cornell Medical Center CTSC. It is a tool for the creation of customized, secure data management systems that include Web-based data-entry forms, reporting tools, and a full array of security features including user and group-based privileges, authentication using institution LDAP system, with a full audit trail of data manipulation and export procedures. REDCap is maintained on CTSC-owned servers that are backed up nightly and support encrypted (SSL-based) connections. Nationally, the software is developed, enhanced, and supported through a multi-institutional consortium led by the Vanderbilt University CTSA.

11.1.2 Smart Watches, Tablet Computers and Internet Capable Devices

Subjects will be provided with Garmin wearable devices. Garmin devices will function as a typical Garmin device. Data will be exported from the Garmin devices directly onto an ITS-tagged, WCMC-issued computer. It will then be transferred onto our WCMC server and deleted from the computer. We will codify data in order for us to conduct data analysis and to share with subjects and their physicians.

Although the devices will be used primarily to collect step-count, we will collect all relevant health data the device provides, including, but not limited to calories burned, floors climbed, and distance traveled.

Phillips internet capable tablet computers will be provided to subjects for remote monitoring. These devices are already in use in the HFpEF Program.

11.2 Regulatory Considerations

11.2.1 Institutional Review Board/Ethics Committee Approval

As required by local regulations, the Investigator will ensure all legal aspects are covered, and approval of the appropriate regulatory bodies obtained before study initiation.

Before initiation of the study, the protocol, the ICF, other written material given to the subjects, and any other relevant study documentation will be submitted to the appropriate Ethics Committee. Written approval of the study and all relevant study information must be obtained before the study center can be initiated. Any necessary extensions or renewals of IEC/IRB approval must be obtained for changes to the study, such as amendments to the protocol, the ICF, or other study documentation. The written approval of the IEC/IRB together with the approved ICF must be filed in the study files. The Investigator will report promptly to the IEC/IRB any new information that may adversely affect the safety of the subjects or the conduct of the study. The Investigator will submit written summaries of the study status to the IEC/IRB as required. On completion of the study, the IEC/IRB will be notified that the study has ended.

All agreed protocol amendments will be clearly recorded on a protocol amendment form and will be signed and dated by the original protocol approving signatories. All protocol amendments will be submitted to the relevant institutional IEC/IRB for approval before implementation, as required by local regulations. The only exception will be when the amendment is necessary to eliminate an immediate hazard to the trial subjects. In this case, the necessary action will be taken first, with the relevant protocol amendment following shortly thereafter. Weill Cornell Medicine must approve all consent form changes prior to local IRB submission. Relevant study documentation will be submitted to the regulatory authorities of the participating countries, according to local/national requirements, for review and approval before the beginning of the study. On completion of the study, the regulatory authorities will be notified that the study has ended.

11.2.2 Ethical Conduct of the Study

The Investigators and all parties involved should conduct this study in adherence to the ethical principles based on the Declaration of Helsinki, GCP, ICH guidelines and the applicable national and local laws and regulatory requirements.

This study will be conducted under a protocol reviewed and approved by the applicable ethics committees and investigations will be undertaken by scientifically and medically qualified persons, where the benefits of the study are in proportion to the risks.

11.2.3 Informed Consent

The investigator or qualified designee must obtain documented consent according to ICH-GCP and local regulations, as applicable, from each potential subject or each subject's legally

authorized representative prior to participating in the research study. Subjects who agree to participate will sign the approved informed consent form and will be provided a copy of the signed document.

The initial ICF, any subsequent revised written ICF and any written information provided to the subject must be approved by IRB prior to use. The ICF will adhere to IRB/IEC requirements, applicable laws and regulations.

11.2.4 Compliance with Trial Registration and Results Posting Requirements

Under the terms of the Food and Drug Administration Modernization Act (FDAMA) and the Food and Drug Administration Amendments Act (FDAAA), the Sponsor-Investigator of the trial is solely responsible for determining whether the trial and its results are subject to the requirements for submission to <http://www.clinicaltrials.gov>. Information posted will allow subjects to identify potentially appropriate trials for their disease conditions and pursue participation by calling a central contact number for further information on appropriate trial locations and trial site contact information.

11.2.5 Record Retention

Essential documents are those documents that individually and collectively permit evaluation of the study and quality of the data produced. After completion of the study, all documents and data relating to the study will be kept in an orderly manner by the Investigator in a secure study file.

12. Statistical Considerations

To provide statistics to the subjects when sharing key outcomes, we will compare PROs between Periods A (On) and Periods B (Off) using a linear or generalized linear mixed effects model that will include the fixed effects of beta-blocker, treatment effect (A vs B), period effect (1, 2, 3, 4 etc.) and a patient-level random intercept to account for within-patient repeated measurements. The period fixed effect will estimate the effects of down-titration/up-titration and the time-dependent treatment effect will estimate On vs. Off effect. We will also explore period-specific fixed effects for treatment and compare the models using Akaike Information Criterion. As an exploratory analysis, we will also test the pattern of activity as a function of time in specialized statistical models called functional data model.

Power: The study team will have 80% power to detect a within-patient difference of 1.1 standard deviations in the four outcomes at an $\alpha=1.67\%$ (after controlling for Type I error inflation due to three outcomes). While power for these analyses will be modest, they will provide pilot data necessary for a future proposal to the National Institute of Health (NIH) and/or Patient-Centered Outcomes Research Institute (PCORI) to conduct a larger multi-center randomized controlled trial to determine whether discontinuation of BB in HFpEF can improve outcomes relevant to older adults including function and quality of life.

Power: The co-primary objective is to determine features of a feasible and pragmatic protocol for deprescribing N-of-1 trials, which will be done through an iterative stakeholder-engaged process (C.1.2). The goal is *not* to establish safety and/or efficacy here. Thus, power calculations for this Aim are less relevant.

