| Study Description: | We will determine whether N-of-1 trials, as a pragmatic, patient-centered approach to medication optimization that can overcome key barriers of deprescribing, can lead to increased subject confidence regarding the decision to continue or discontinue beta-blockers in older adults with Heart Failure with Preserved Ejection Fraction (HFpEF). |
| Sample Size: | N=16 |
| Enrollment: | This study will enroll 16 subjects. |
| Study Population: | Subjects will be recruited from the HFpEF Program, as well as from the Cardiology, Heart Failure, Geriatrics and/or Internal Medicine clinics at Weill Cornell Medicine. |
| Enrollment Period: | 30 Months |
| Study Design: | This is an unblinded NIH Stage 1 of Behavioral Intervention Development trial, using a Crossover intervention model. We will enroll 16 subjects and we will conduct four rounds of N-of-1 trials with four subjects each. We will use a two-arm crossover titration/reversal design (On [A] vs. Off [B]) with up to 4 periods. Subjects will be randomized to either ABAB or BABA (see Figure 1 below). Each period will last up to 6 weeks, allowing for sufficient time for up-titration and onset of drug action, and down-titration and washout. Each subject will have the option to participate in less (2-3) or more periods (5-6) depending on whether they need additional information to make an informed decision about continuing or discontinuing their beta-blocker at the end of this trial. The intervention drug will be beta-blockers, previously prescribed to the subjects by their physician. We have developed a titration algorithm, where we will reduce the dose of each beta-blocker by 50% every week. |
| Description of Sites/ Facilities Enrolling | |
| Subjects: | Enrollment will only be at Weill Cornell Medicine. |
| Study Duration: | Estimated Primary Completion Date of December 2022 |
| Subject Duration: | 1 Year |
| Study Agent/Device Name | Not applicable |

Intervention Description:

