2.2 Rationale

High medication burden among older adults with multiple chronic conditions including those with heart failure is a growing problem in the United States that can negatively impact the health and wellbeing of older adults. Deprescribing (or medication discontinuation) has emerged as a strategy to improve outcomes in older adults with multiple chronic conditions and high medication burden but is underutilized. With this project, we will refine an innovative pragmatic subject-centered approach (N-of-1 trials) to medication optimization in older adults, thereby improving the health and wellbeing of older adults with multiple chronic conditions.

In [name] clinical experience as Director of the HFpEF Program for the Aging, he has found that some patients feel better with beta-blockers while others feel worse. This idea is supported by opposing pathophysiologic mechanisms highlighted in the literature—on the one hand, beta-blockers can slow down heart rate, improve left ventricular filling, and thus improve cardiac output and overall functioning. On the other hand, beta-blockers can exacerbate chronotropic incompetence, worsen cardiac output, and reduce exercise tolerance. Beta-blockers are also a common cause of adverse drug reactions and can worsen function in some older adults. There is no readily discernable way to determine which patients will feel better and which will feel worse. Although the benefits of beta-blockers in HF with reduced ejection fraction are well documented, RCTs of beta-blockers in HFpEF have been neutral to date, failing to consistently improve or worsen long-term outcomes including mortality and hospitalization rate. Thus, beta-blocker use in HFpEF is a well-suited and clinically relevant model for developing a subject-centered approach to medication optimization.

N-of-1 trials offer a potentially transformative approach to deprescribing. Unlike traditional population-based clinical trials, N-of-1 trials are conducted within a single subject, using multiple crossover design experiments to compare different treatments.

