2.3.2 Known Potential Benefits

For some, continuing beta-blockers may be beneficial: Beta-blockers slow down heart rate, improve left ventricular filling and thus improve cardiac output and overall functioning. They can function as anti-hypertensive and may suppress arrhythmias.

For others, stopping beta-blockers may be beneficial: Beta-blockers can exacerbate chronotropic incompetence, worsen cardiac output, and reduce exercise tolerance. Beta-blockers are also a common cause of adverse drug reactions and can worsen function in some older adults. Beta-blockers can also contribute to undesirable symptoms like fatigue and sexual dysfunction.

Subjects may specifically benefit from this study by gaining insight on the individual-level short-term effects of beta-blockers. This information could then help subjects determine whether they wish to continue or discontinue beta blockers, potentially contributing to increased decision confidence and subject activation, and possibly improving quality of life.

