3.1 Overall Design

This single site, NIH Stage I of Behavioral Intervention Development trial will extend principles of subject-centered care (a pillar of caring for older adults with MCC) to medication management by producing a broadly applicable approach (N-of-1) that can bypass the inherent limitations of randomized controlled trials which provide average treatment effects and limited data on the effects of medication for a single individual; and thereby facilitate personalized pharmacotherapy and therapeutic precision by determining the optimal therapy for the individual in the face of the inherent complexity and heterogeneity of older adults related to variability in clinical phenotype, drug metabolism, responsiveness to therapy, and health priorities.

This study will also formalize a process that can increase subject involvement and incorporate shared decision making into medication management, an important priority in cardiovascular medicine.

We will conduct N-of-1 trials using a two-arm crossover withdrawal/reversal design (On [A] vs Off [B]) with up to 4 periods. Subjects will be randomized to either Arm1/ABAB or Arm2/BABA (see Figure 1 above). After the initial period (Period 1), each subject will crossover to the other arm and continue in that arm for up to 6 weeks (Period 2). This may be repeated for two more periods for a total of 4 periods; each period will last up to 6 weeks, permitting sufficient time for up-titration and onset of drug action, and down-titration and washout. If the subject and the principal investigator make a final decision to discontinue or continue the beta-blocker at the end of a period, the end of intervention phase will begin at the end of that period visit. For the remainder of the protocol, we refer to “end of intervention” as period 4, but this can be changed based on when a final decision is made about the beta-blocker. The end of intervention visits can occur at any of the periods. The minimum number of periods will be 2 (AB or BA). If the subject wishes to collect more data, then additional periods may be added in an alternating fashion (ABAB or BABA). Accordingly, the number of periods will be an adaptive component of the protocol.

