Per subject feedback, we may eliminate the use of wearable devices or modify subject reported outcome questionnaires. We may also give caregivers the opportunity to share any feedback they may have. We will ask the subjects for permission to discuss the study with their caregivers. We will also ask the subjects for permission to contact and discuss the trial with their primary care provider or their primary cardiologist.

At the conclusion of the intervention phase, and possibly at the end of each intervention period, we will provide subjects with visual analogies of their physical function and subject reported outcomes data. These data will be discussed with them to help them determine if they would like to continue or discontinue their beta-blockers for the foreseeable future.

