4. *Exercise capacity (via peak oxygen consumption during exercise).* A general linear mixed effects model will be used, comparing VO2 of the On and Off arms.
5. *Patient-reported outcomes (PROs).* A general linear mixed effects model will be used, comparing each patient-reported outcome domain (HF-specific quality of life, fatigue, depression, anxiety, sleep, physical function, social role, and pain) of the On and Off arms. The study team will analyze data from the timeframe during which BB is completely stopped (“Off” when participating in the Off-arm) and at usual dose (“Full dose” when participating in the On-arm); this will occur during weeks 5 and 6 of each Period, or the last two weeks of the period. (see Figure 1).
6. *Subject Qualitative Interviews.* Directed content analysis methods will be used to develop relevant categories and themes from interview transcript data. Coding will be conducted through the coding platform Dedoose. Transcripts will be analyzed by two team members, consulting additional members to establish consensus where needed. Inter-rater reliability between coders will be established using a Cohen's Kappa score.

To provide statistics to the subjects when sharing key outcomes, we will compare PROs between Periods A (On) and Periods B (Off) using a linear or generalized linear mixed effects model that will include the fixed effects of beta-blocker, treatment effect (A vs B), period effect (1, 2, 3, 4 etc.) and a patient-level random intercept to account for within-patient repeated measurements. The period fixed effect will estimate the effects of down-titration/up-titration and the time-dependent treatment effect will estimate On vs. off effect. We will also explore period-specific fixed effects for treatment and compare the models using Akaike Information Criterion. As an exploratory analysis, we will also test the pattern of activity as a function of time in specialized statistical models called functional data model.

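### The model that supplies statistics to subjects has one On–Off effect for all patients, so its figure is an unlabelled group average, not the subject's own effect

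*Combined protocol and SAP*

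**What the plan says.** Section 12 (Statistical Considerations) introduces the feedback model with the words "To provide statistics to the subjects when sharing key outcomes, we will compare PROs between Periods A (On) and Periods B (Off"), and 12.4.1 repeats it. The terms are fixed effects of beta-blocker, treatment (A vs B) and period, plus "a patient-level random intercept to account for within-patient repeated measurements". The only extension is: "We will also explore period-specific fixed effects for treatment and compare the models using Akaike Information Criterion". The endpoint model at the start of 12.4.1 also has a random intercept only. Neither section describes a random treatment effect, a patient-by-treatment term or a per-patient estimate.

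The stated purpose is individual. Section 2.3.2 says subjects may benefit by "gaining insight on the individual-level short-term effects of beta-blockers". Section 3.1 presents the N-of-1 approach as a way past the limits of "randomized controlled trials which provide average treatment effects and limited data on the effects of medication for a single individual". Section 2.2 says of response to beta-blockers: "There is no readily discernable way to determine which patients will feel better and which will feel worse".

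Section 3.1 also says what else subjects see: their questionnaire answers, plots of how those answers differed between periods, and displays of their physical function and reported outcomes. Of these it says: "These data will be discussed with them to help them determine if they would like to continue or discontinue their beta-blockers".

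**The concern.** The feedback statistic is offered to a subject who is weighing whether to stay on treatment. A reader of Sections 2 and 3 would expect it to describe that subject. Under the written model it describes the average participant, and nothing tells the subject so. Someone whose response differs from the mean would see their own plots next to a common figure that may point the other way, with no explanation. If the model's interval were also shown, it would express uncertainty about the mean and understate uncertainty about that person.

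Timing matters too. Section 3.1 allows a final decision after two periods, and the first subject to get there has no other data to borrow from. The plan does not say what that subject is given.

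**Working it through.** **1. The On–Off contrast in the written model.** For patient i, period j, score k:

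y = μ + u_i + β·Off_ij + π_j + e_ijk.

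In an On–Off comparison u_i cancels and β remains, the same for every i.
- With period-specific treatment effects, β becomes β_j: it varies by period and is still common to all patients.
- If the beta-blocker term means the agent, it is constant within a patient and also cancels.
- With a generalized model, the effect on the link scale, and so its direction, is still common.

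**2. Fitting the model to one subject.** With P periods there are P + 1 columns (intercept, P − 1 period indicators, treatment) but only P distinct rows. In ABAB, for example, Off equals the period 2 indicator plus the period 4 indicator. The rank is 2 of 3 columns with two periods and 4 of 5 with four. Treatment is not estimable from one subject.

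**3. Size if the pooled interval were shown.** Inputs from the documents: two periods (the minimum in 3.1); weekly PROMIS-29 (6.1.2b) analysed over the last two weeks of a period (12.4.1), taken as two scores per period; and n = 4 and n = 16, because the synopsis says "we will conduct four rounds of N-of-1 trials with four subjects each". Assumed: residual SD 1, independent scores, balanced sequences, tau = 0.25, 0.5 or 1.0.

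- A patient's own difference has variance tau² + 1/2 + 1/2 = tau² + 1.
- Mean squared error of the pooled estimate against a contributing subject's own effect: tau²(1 − 1/n) + 1/n.
- Residual df: 4n − n − 2 = 3n − 2. Expected residual variance: s² = [2n + (n − 2)(1 + tau²)]/(3n − 2).
- Half-width: t × √(s²/n), with t = 2.228 (10 df) for n = 4 and 2.013 (46 df) for n = 16.
- Approximate coverage: 2Φ(half-width/RMSE) − 1.

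| n | tau | RMSE | s² | Half-width | Approx. coverage | Simulated |
|---|---|---|---|---|---|---|
| 4 | 0.25 | 0.545 | 1.013 | 1.121 | 96% | 93–94% |
| 4 | 0.5 | 0.661 | 1.050 | 1.142 | 92% | 89% |
| 4 | 1.0 | 1.000 | 1.200 | 1.220 | 78% | 75–76% |
| 16 | 0.25 | 0.348 | 1.019 | 0.508 | 86% | 85% |
| 16 | 0.5 | 0.545 | 1.076 | 0.522 | 66% | 66% |
| 16 | 1.0 | 1.000 | 1.304 | 0.575 | 43% | 43% |

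The formula treats s² as fixed, so it runs high at n = 4; the simulated column is the one to use. Coverage falls as n grows because the interval narrows around the mean while individuals stay as spread out as before.

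**4. Point accuracy.** RMSE against the subject's own effect at two periods, pooled versus patient-specific prediction (tau averaged over a half-normal prior with scale 1 residual SD):
- tau 0.5: 0.66 vs 0.68 (n = 4) and 0.54 vs 0.54 (n = 16).
- tau 1.0: 1.00 vs 0.89 (n = 4) and 1.00 vs 0.79 (n = 16).

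**5. Minor note on the group test.** For the weekly PROMIS-29 domains listed in 12.4.1, the true variance of the pooled estimate is (tau² + 1)/n, while the model uses s²/n. With n = 16 the ratio is 1.25/1.076 = 1.16 at tau 0.5 and 2/1.304 = 1.53 at tau 1.0. Simulated Type I error at nominal 5% is 5.4%, 6.7% and 11.0% for tau 0.25, 0.5 and 1.0. With one score per period there is no inflation (5.0–5.1%).

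**The case against.** The strongest reply is that subjects already get an individual comparison. Section 3.1 gives them their own answers and period-by-period plots and has these discussed explicitly, and the data it says will support the decision are those displays. This stands. A reader might infer that each subject is shown only the group mean when deciding; the documents do not support that. No section says that the model coefficient drives the decision.

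A reader might also take the coverage figures as a property of the plan. They are not. The plan promises statistics and mentions no interval, tau is assumed, and at tau/SD 0.25 with 4 subjects the shortfall is small.

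Third, the model change may bring little accuracy. Step 4 shows none at tau/SD 0.5 with two periods, and with a smaller tau a poorly chosen prior can make the prediction slightly worse than the mean. In a four-period illustration (16 patients, residual SD and tau both 5, mean effect 0, 2 or 4), the common figure had the wrong sign for 44%, 34% and 21% of patients. The random-slope estimate had 22%, 19% and 14%, and the subject's raw difference 20%, 18% and 15%. The model therefore adds little to the raw data in direction. Section 2.3.3 reports that 8 of 9 earlier patients felt better off treatment. That implies mean/tau of 1.22, where the gain in sign is about nil. The exact 95% interval for 8 of 9 (52% to 99.7%) corresponds to mean/tau of 0.04 to 2.8, so it does not settle the matter.

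None of this gives the written model a patient-specific effect or labels its output.

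**Conclusion.** The concern holds for the model-based statistic and for nothing else that is shared. The result in steps 1 and 2 is structural and needs no assumption: one On–Off effect for all patients, and no way to fit the model to one subject. This conflicts with the individual-level purpose in 2.2, 2.3.2 and 3.1, and the figure carries no label.

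The consequence is conditional. It rests on an unknown tau, on two scores per period and, for coverage, on an interval being shown. At tau/SD 0.5 with two periods the benefit of the fix is correct labelling and honest uncertainty, not a better point estimate. The trial is not invalidated, but the point should be fixed.

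The Type I error note is minor. A reader might extend it to every outcome. It does not apply to outcomes with one value per period over two periods, such as peak VO2, and cognitive function (SF-6a) is not in the list of PRO domains in 12.4.1.

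**What to change.** In the feedback model of Sections 12 and 12.4.1:
- Add a patient-level random treatment effect to the existing terms. Give each subject the patient-specific On–Off prediction with its uncertainty, beside the own-data plots already planned.
- Label any pooled figure 'average of all participants so far'.
- Until the model can be fitted, give early subjects their own data only, or prespecify a prior for tau.
- For two-period subjects, state that separating treatment from period relies on the other subjects.

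If the model is left unchanged, the minimum fix is the label. For the minor note, the weekly PROMIS-29 domains can be analysed with the same random effect, or as per-patient mean differences adjusted for sequence (simulated Type I error 4.8–5.0%).

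The cost is SAP wording and code, with no new data. At two periods the individual uncertainty is about 1.6 times as wide as the pooled interval with 4 subjects and 2.2 to 2.5 times with 16. A prior or fallback must also be chosen, and it matters: at two periods, with prior scales from 0.5 to 2 and tau/SD of 0.5 and 1.0, coverage of the patient-specific interval ran from 85% to 99.7%.

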6.1.1 Baseline In-Person Visit

- Informed consent
- Randomization
 - Eligible subjects will be randomly assigned to into Arm 1 (ABAB) or Arm 2 (BABA) with a 1:1 ratio using a computer-generated randomization scheme developed by the data manager. Arm 1 will be on an On-Off-On-Off (ABAB) drug scheme, while Arm 2 will be Off-On-Off-On (BABA)
- Demographics
- Medication Inventory
- Baseline beta-blocker use
- Physical Exam, including vital signs
- Central blood pressure assessment via the UScom BP+ device
 - This device measures central and brachial blood pressure and blood pressure waveforms at the heart, as well as in the arm.
- Electrocardiogram
- Blood draw for Troponin & NT-proBNP
- Blood draw for future research
- Six-Minute Walk Test
- Exercise test used to assess aerobic capacity endurance. The distance covered over 6 minutes is used as the outcome by which to compare changes in performance capacity.
- Short Physical Performance Battery
 - Combines the results of gait speed, chair stand and balance tests as a predictive tool for possible disability and can aid in the monitoring of function in older people
 - Gait Speed: assesses the subject's lower extremity function
 - Chair Rise: assesses core strength
 - Balance Test: assess the subject's ability to stand unassisted without the use of a cane or walker
- Qualitative interview on understandability of study purpose and design
- Typology Questionnaire
- Health Literacy Questions
- Number Literacy Questions
- Short Graph Literacy
- EQ5D Visual Analogue Scale
- PROMIS-29
- PROMIS-SF 6A
- PROMIS-Sexual Function
- KCCQ-12
- Decision Making Outcomes Questionnaires
 - Decision Conflict Scale
 - Decision Conflict Subscale
 - Patient Activation Measure (PAM) Survey
 - Shared Decision Making Questionnaire
 - Revised Patient Attitude Towards Deprescribing Questionnaire (rPATD)

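### In ABAB/BABA, each exploratory period-specific treatment effect compares Arm 1 with Arm 2; cycle-specific effects would keep the question within patients

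*Combined protocol and SAP*

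**What the plan says.** Section 12, repeated at the end of Section 12.4.1, introduces a mixed model for PROs with this purpose: "To provide statistics to the subjects when sharing key outcomes, we will compare PROs between Periods A (On) and Periods B (Off". It has a treatment effect, "period effect (1, 2, 3, 4 etc.) and a patient-level random intercept to account for within-patient repeated measurements". No sequence (arm) term is listed. The next step is: "We will also explore period-specific fixed effects for treatment and compare the models using Akaike Information Criterion". Nothing states which figures are reported if AIC prefers the larger model.

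On the design, the synopsis says "This study will enroll 16 subjects". Section 6.1.1 gives the allocation, "Eligible subjects will be randomly assigned to into Arm 1 (ABAB) or Arm 2 (BABA) with a 1:1 ratio", and the sequences: "Arm 1 will be on an On-Off-On-Off (ABAB) drug scheme, while Arm 2 will be Off-On-Off-On (BABA". Section 3.1 lets subjects stop early: "The minimum number of periods will be 2 (AB or BA". It also allows five or six periods.

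The numbered endpoint analyses in Section 12.4.1 use a separate model with treatment, period, carry-over and a random intercept, and no AIC step.

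**The concern.** The common On-Off effect compares each subject with himself or herself. A treatment effect allowed to differ by period cannot do that, because within one period no subject is both On and Off. It can only compare the two arms, and a patient random intercept does not change this. A chance difference between two groups of about eight then appears as an On-Off effect, positive in some periods and negative in the others.

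The AIC step therefore cannot distinguish a drug effect that changes over time from a chance arm difference. This matters because the model is meant to produce figures for subjects. Section 3.1 says that PRO comparisons between periods will be discussed with subjects as they decide about their beta-blocker, possibly at the end of each period.

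**Working it through.** The plan gives no figure for this step, so there is none to reproduce. Its power statement concerns another analysis and is not used here.

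**Inputs.** From the documents: 16 subjects, 1:1 allocation, sequences ABAB and BABA, two to six periods. Assumed: 8 per arm, complete data unless stated, and within-patient correlation ρ from 0.3 to 0.8 (the documents give none). Standard errors are in units of the outcome SD for one period value.

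**1. What the period-specific effect is.** Let m1p and m2p be the arm means in period p, and let s_p be +1 in odd periods and -1 in even periods. With four periods the model has 4 period effects and 4 treatment effects for 8 cell means (2 and 2 for 4 cell means with two periods), so it is saturated. The fitted effect is

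τ_p = s_p × (m1p − m2p).

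Maximum likelihood fits to simulated data matched this to four decimals.

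**2. How an imbalance enters.** If the true effect is τ and the arms differ by δ, then τ_p estimates τ + s_p × δ. With δ = 0.5 SD:

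| True effect τ | Period 1 | Period 2 | Period 3 | Period 4 |
|---|---|---|---|---|
| 0 | +0.5 | −0.5 | +0.5 | −0.5 |
| 0.3 | +0.8 | −0.2 | +0.8 | −0.2 |
| 0.5 | +1.0 | 0 | +1.0 | 0 |

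The contribution of δ always alternates. The On-Off effects themselves change sign only when δ exceeds τ in size. Averaged over an even number of periods δ cancels, so the mean of the τ_p is the within-patient estimate.

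**3. Precision.**

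- One period-specific effect: sqrt(1/8 + 1/8) = 0.50, with no ρ in the formula.
- Common effect, four periods: sqrt((1 − ρ)/16).
- Common effect, two periods: sqrt((1 − ρ)/8).

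| ρ | Common, 4 periods | Common, 2 periods | One period-specific effect |
|---|---|---|---|
| 0.3 | 0.21 | 0.30 | 0.50 |
| 0.5 | 0.18 | 0.25 | 0.50 |
| 0.7 | 0.14 | 0.19 | 0.50 |
| 0.8 | 0.11 | 0.16 | 0.50 |

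At ρ = 0.7 the average of the four period-specific effects has standard error 0.137, the same as the common effect.

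**4. How often AIC prefers the larger model when the effect is constant.** AIC prefers it when the likelihood-ratio statistic exceeds twice the number of extra parameters.

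- Four periods, 3 extra: P(χ²₃ > 6) = 0.112.
- Two periods, 1 extra: P(χ²₁ > 2) = 0.157.

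At this trial's size (1,500 simulated trials per scenario, ρ of 0.5 and 0.7, true effect 0, 0.3 or 0.5 SD) the rates were 14.9% to 17.5% with four periods and 17.3% to 20.7% with two. Among the trials where AIC preferred the larger model, the estimated signs alternated throughout in 28% to 64% (four periods) and 80% to 100% (two periods).

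**5. The cycle-specific alternative.** A cycle is one On and one Off period, so δ cancels within it for subjects who complete it. Its standard error with all 16 is sqrt((1 − ρ)/8), or 0.19 at ρ = 0.7. Generalised least squares at ρ = 0.7, with stopping spread evenly over the arms, gives:

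| Periods completed (assumed) | Cycle 2 effect | Period 3 effect | Period 4 effect |
|---|---|---|---|
| All 16 complete four | 0.19 | 0.50 | 0.50 |
| 8 stop after two, 8 complete four | 0.27 | 0.60 | 0.60 |
| 8 / 4 / 4 complete two / three / four | 0.33 | 0.60 | 0.74 |

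**The case against.** The strongest reply is that the text commits to very little: it says explore and compare. The model stated first has one On-Off effect, and no sentence says that the AIC winner replaces it. A reader might infer that AIC can swap out the reported result. The documents do not say so; they only leave the reporting rule unstated. That stands.

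A reader might also infer that the period-specific model discards the within-patient information. It does not: with complete data the average of its effects equals the common estimate, with the same precision. Only the single-period figures are weak. Nor must the On-Off effects reverse every six weeks, as the second row block of the imbalance table shows. The 11% and 16% are AIC's general rates for three or one extra parameters and are not peculiar to this design.

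The endpoint analyses of vitals, step count, physical performance, peak VO2 and PRO domains have no AIC step and are untouched. With two-period data the contrast is also algebraically the same as a sequence or carry-over contrast, so it is not a new quantity there.

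Finally, cycle-specific effects have limits. Two-period subjects have no second cycle, and Section 3.1 creates three-period subjects with only half of one. Those who go on after Period 2 do so by their own decision.

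All of this narrows the consequence. It leaves the aliasing of treatment with arm inside each period, and a precision gap that persists under early stopping: 0.27 to 0.33 SD against 0.60 to 0.74 SD in the two scenarios above.

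**Conclusion.** The point holds as a minor defect in an exploratory step. In this design a period-specific treatment effect is a between-arm contrast with a standard error of 0.50 SD. The common effect has 0.11 to 0.21 SD with four periods, or 0.16 to 0.30 SD with two, for correlations from 0.8 down to 0.3. AIC will prefer the period-specific model in roughly one trial in nine (four periods) or one in six (two periods) in large samples when the effect is constant, and somewhat more often at 16 subjects.

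These figures assume exact 8:8 allocation and complete data. No blocking is stated, and simple randomisation gives exactly 8:8 in about 20% of cases (12,870/65,536). With early stopping the later contrasts rest on fewer subjects and cannot be estimated if only one arm remains.

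The documents do not support reading this as a threat to the co-primary or secondary endpoint results, or as a planned replacement of the On-Off effect. The gap is an exploratory model that cannot answer its own question, together with a missing reporting rule.

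**What to change.** In the paragraph that appears in both Section 12 and Section 12.4.1:

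- Replace period-specific with cycle-specific treatment effects (Periods 1-2 versus Periods 3-4).
- Fit both models by maximum likelihood for the AIC comparison, since they differ in fixed effects.
- State that the common within-patient On-Off effect is what is reported, whatever AIC shows.
- Label the cycle-specific effects exploratory, and give the number of subjects contributing to each.

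This costs a sentence or two and needs no extra data, visits or subjects. There is a drawback: cycle 2 is informed mainly by subjects who choose to continue past Period 2, a self-selected group. At an assumed correlation of 0.7 its standard error is 0.19 SD only if all 16 complete four periods, and about 0.27 to 0.33 SD if half stop after Period 2. For subjects with two periods only, no within-patient look at change over time is possible, and the plan should say so.
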